## 1.4 STUDY PLAN

This is a multicenter, 30-week, randomized, double-blind, placebo-controlled Phase 3 study consisting of 3 study periods:

- An up to 3-week screening period (with a minimum of 10 days)
- A 30-week double-blind, placebo-controlled treatment period, for efficacy and safety assessment
- A 6-week posttreatment follow-up period to collect safety information after last dose of IMP

The maximum study duration per participant will be 39 weeks. The graphical study design is shown in [Figure 1](#).

**Figure 1 - Study design overview**

Abbreviations: EOS, End of Study; EOT, End of Treatment; R, Randomization; SU, sulfonylurea.  
Note: The telephone symbol is used to designate visits conducted by telephone interview.

The end of the study is defined as the date of the last visit of the last participant in the study.

### 1.5 MODIFICATIONS TO THE STATISTICAL SECTION OF THE PROTOCOL

Not applicable.

### 1.6 STATISTICAL MODIFICATIONS MADE IN STATISTICAL ANALYSIS PLAN

Due to study early termination, the efficacy evaluations originally planned in the protocol were no longer considered to be relevant and were not performed. PK and ADA samples were not analyzed thus no analyses were planned. This is a simplified statistical analysis plan (SAP) for the purpose of synopsis clinical study report (CSR).

## 2 STATISTICAL AND ANALYTICAL PROCEDURES

### 2.1 ANALYSIS ENDPOINTS

#### 2.1.1 Demographic and baseline characteristics

The Baseline value (with the exception of serum creatinine and eGFR) is defined as the last available value prior to the first dose administration of IMP or the last available value on or before the date of randomization if not treated with the study treatment.

For serum creatinine and eGFR, baseline is defined as the average of all values before the first dose of double-blind IMP for those randomized and exposed or before randomization for those who were randomized but never exposed to IMP.

All Baseline safety parameters (apart from those listed below) are presented along with the on-treatment summary statistics in the safety sections ([Section 2.4.4](#)).

Summary statistics of baseline efficacy parameters by treatment group and overall will be provided for the randomized population.

#### *Demographic characteristics*

Demographic variables are gender (Male, Female), race (Asian, Black or African American, White, Multiple, other), age in years (quantitative and qualitative variable: <50, ≥50 and <65, ≥65 and <75, and ≥75 years), ethnicity (Hispanic or Latino, not Hispanic or Latino, Unknown, and Not reported), country, Baseline body mass index (BMI) (quantitative and qualitative variable: <30, ≥30 and <40, ≥40kg/m^2), randomization strata [HbA1c at screening (<8.0%, ≥8.0%); SU use at screening (Yes/No)].

Participants counted as multiple races will not be counted in other race categories.

#### *Medical history*

Medical history includes medical or surgical history.

This information will be coded using the version of Medical Dictionary for Regulatory Activities (MedDRA) currently in effect at the time of database lock.

#### *Disease characteristics at Screening or Baseline*

Diabetes history includes:

- Duration of diabetes (years) derived as: (Date of informed consent – Date of diagnosis of diabetes + 1)/365.25
- Categories of duration of diabetes (<10 years, ≥10 years)

- Age at diagnosis of diabetes (years) derived as: Year of diagnosis of diabetes – Year of birth
- eGFR (mL/min/1.73 m^2) at baseline
- Categories of eGFR at baseline (in ml/min/1.73 m^2) ( $\geq 90$  (normal),  $\geq 60$  and  $< 90$  (mild decrease in GFR),  $\geq 30$  and  $< 60$  (moderate decrease in GFR),  $\geq 15$  and  $< 30$  (severe decrease in GFR),  $< 15$  (end stage renal disease))
- Antidiabetic medication at the time of screening (Metformin, Metformin and Sulfonylurea)
- Duration of Metformin and Sulfonylurea (years) at screening
- Daily dose of Metformin (mg) at screening

Any technical details related to computation, dates, and imputation for missing dates are described in [Section 2.5](#).

### 2.1.2 Prior or concomitant medications

Any medication or vaccine (including over-the-counter or prescription medicines, vitamins, and/or herbal supplements) that the participant is receiving at the time of enrollment or during the study must be recorded in the corresponding case report form page.

All medications will be coded using the World Health Organization-Drug Dictionary (WHO-DD) using the version currently in effect at the time of database lock.

Medications will be classified into the following 3 groups:

- Prior medications are those the participant used prior to first IMP administration. Prior medications can be discontinued before first IMP administration or can be ongoing during the treatment phase.
- Concomitant medications are any treatments received by the participant concomitantly to the IMP(s), from first dose to the end of treatment +30 days (+7 days for antidiabetic drugs). A given medication can be classified both as a prior medication and as a concomitant medication. Concomitant medications do not include medications started during the posttreatment period (as defined in the observation period in [Section 2.1.4](#)).

Post-treatment medications are those the participant took in the period running from the 31st day (8 days for antidiabetic drugs) after the last injection of IMP up to the end of the study.

**Background medication** includes metformin alone or in combination with SU. Background metformin and SU are considered as Non-IMPs (NIMP). Metformin and SU (commercial formulations) will be administered orally according to the locally approved label.

**Rescue medication(s)** is considered Non-IMP treatment. Except for GLP-1 RA and DPP-4 inhibitors, any approved medications (including increase of prior metformin or SU dose) can be prescribed to treat the hyperglycemia. Increasing the SU dose up to the Screening dose level is not

considered as rescue therapy in participants whose SU dose was temporarily decreased for HbA1c <8.0% at Week -1 or for hypoglycemia.

### **Prohibited medication**

The following treatments are prohibited during the study (including during the screening period and the 30 weeks of treatment period).

- Initiation of any antidiabetic agents, other than the IMP, or increase in dose of preexisting oral antidiabetic drugs (OAD), before pre-rescue assessments and initiation of rescue therapy (short-term use [ $<10$  consecutive days] of short-acting insulin for treatment of acute illness or surgery is allowed)
- Initiation of any GLP-1 RAs (eg, exenatide, liraglutide, dulaglutide, or semaglutide) and DPP-4 inhibitors (eg, sitagliptin, saxagliptin, vildagliptin, or linagliptin)
- Initiation of any prescription weight loss drugs (eg, phentermine, lorcaserin, or orlistat)
- Gastric surgery or other gastric procedures for weight loss
- Systemic use of glucocorticoids for more than 10 consecutive days (topical, nasal spray, and inhaled or intra-articular applications are allowed)
- Any investigational drug other than IMP for this study

Similar to concomitant medications, summary table for prohibited medications will be provided as well.

Any technical details related to computation, dates, imputation for missing dates are described in [Section 2.5](#).

### **2.1.3 Efficacy endpoints**

Efficacy endpoints are defined in [Section 2.1.3.1](#), [Section 2.1.3.2](#), [Section 2.1.3.3](#).

Efficacy endpoints will be summarized in conventional units for HbA1c (%) and weight (kg), and standard international units for FPG (mmol/L).

#### **2.1.3.1 Primary efficacy endpoint**

- Change in HbA1c (%) from Baseline to Week 30

#### **2.1.3.2 Secondary efficacy endpoints**

- Number of participants with HbA1c <7.0% at Week 30
- Change in FPG from Baseline at Week 30
- Change in body weight from Baseline at Week 30

### **2.1.3.3 Exploratory efficacy endpoint(s)**

- Changes in 7-point SMPG profiles (mmol/L, mg/dL: mean 24-hour SMPG) from Baseline to Week 30
- Change in plasma glucose excursions (2-hours PPG minus preprandial plasma glucose at breakfast, lunch, and dinner) based on 7-point SMPG data from Baseline to Week 30
- Number of participants with rescue therapy used until Week 30
- Time to initiation of rescue therapy (weeks)

### **2.1.4 Safety endpoints**

The safety analysis will be based on the reported AEs, hypoglycemia and other safety information, such as, vital signs.

#### ***Observation period***

The observation period will be divided into 3 main segments:

- The **pretreatment** period is defined as the time from informed consent up to the time of first injection of IMP
- The **on-treatment** period is defined as the time from the first injection of the IMP up to 30 days (7 days for hypoglycemia) after the last injection of the IMP
- The **posttreatment** period is defined as the period from the end of the whole on-treatment period

The **on-study observation** period is defined as the time from first injection of IMP up to either the last protocol-planned visit or the date of last available information if participants discontinue the study prematurely (ie, the date collected on e-CRF page “Completion of End of Study/Follow-up”), whichever is later.

#### **2.1.4.1 Adverse events observation period**

The AE observations will be classified per the observation periods of safety data as defined above into the following:

- **Pretreatment AEs** are AEs that developed or worsened or became serious during the pretreatment period
- **Treatment-emergent AEs (TEAEs)** are AEs that developed or worsened or became serious during the on-treatment period
- **Posttreatment AEs** are AEs that developed or worsened or became serious during the posttreatment period

All AEs (including serious adverse events (SAE), AESIs, and AEs requiring specific monitoring) will be coded to a lower-level term (LLT), preferred term (PT), high-level term (HLT), high-level

group term (HLGT), and associated primary system organ class (SOC) using the version of MedDRA currently in effect at the time of database lock.

Adverse events of special interest (AESI) include the following terms:

- Pregnancy of a female participant entered in a study as well as pregnancy occurring in a female partner of a male participant entered in a study with IMP/NIMP
- Symptomatic overdose (serious or non-serious) with IMP/NIMP
- Increase in alanine aminotransferase (ALT) >3 x upper limit normal (ULN)

Adverse events requiring specific monitoring (AERSM) include the following terms:

- Severe gastrointestinal (GI) events
- Severe hypoglycemia
- Pancreatic events (including abnormal values of pancreatic enzymes, pancreatitis and pancreatic neoplasm)
- Selected cardiovascular events (CV death, MI, stroke, heart failure leading to hospitalization, unstable angina, and transient ischemic attack [TIA])
- Calcitonin increase >5.9 pmol/L (20 pg/mL) and thyroid C-cell neoplasm
- Acute renal failure
- Diabetic retinopathy complications
- Severe injection site reaction
- Severe allergic reactions
- Severe immune complex disease

Independent Clinical Endpoint Committee(s) (CEC) will review, assess, and/or adjudicate all events of death, selected CV events and pancreatic events.

#### **2.1.4.2 Deaths**

Deaths will be categorized according to the observation periods defined below.

- **Death on-study:** Deaths occurring during the on-study observation period
- **Death on-treatment:** Deaths occurring during the on-treatment period
- **Death post-study:** Deaths occurring after the end of the study (end of on-study observation period)

### **2.1.4.3 Laboratory safety variables**

Clinical laboratory data consists of blood analysis, including hematology, clinical chemistry and urinalysis. Clinical laboratory values will be summarized in both standard international units and conventional units (US), when applicable.

Blood samples for clinical laboratories will be collected at designated visits (see Schedule of Activities in [Appendix B](#)). The following laboratory parameters will be measured at central laboratory:

- Hematology
  - Red blood cells and platelets: Platelet count, Red blood cell count, Hemoglobin, Hematocrit
  - White blood cells: White blood cell count, differential count (Neutrophils, Lymphocytes, Monocytes, Eosinophils, Basophils)
- Clinical chemistry
  - Pancreatic enzymes: Amylase, Lipase
  - Electrolytes: Potassium, Sodium
  - Renal function: Creatinine, Estimated glomerular filtration rate (MDRD formula)
  - Liver function: ALT, Aspartate aminotransferase (AST), Alkaline phosphatase (ALP), Total bilirubin
  - Lipid profile: Triglyceride, Total cholesterol, Low-density lipoprotein cholesterol, High-density lipoprotein cholesterol (For triglycerides, only values assessed in fasted participants will be analyzed)
  - Calcitonin

Technical formulas are described in [Section 2.5.1](#).

### **2.1.4.4 Vital signs variables**

Vital signs include sitting heart rate (bpm), and sitting systolic and diastolic blood pressures.

### **2.1.4.5 Electrocardiogram variables**

The 12-lead ECG recording will be performed locally at Randomization, Week 12, and Week 30. Investigator's interpretation of normal and abnormal will be reported in the eCRF.

### **2.1.4.6 Hypoglycemia**

During the study, participants are to be instructed to document any hypoglycemic episodes in their study diary. Hypoglycemia will be reported in the specific eCRF page with onset date and time, symptoms and/or signs, the SMPG value if available, and the treatment of the hypoglycemia.

Hypoglycemia fulfilling the seriousness criteria will be documented, in addition, on the SAE form in the eCRF.

Hypoglycemic events will be categorized as follows:

- **Severe hypoglycemia:** Severe hypoglycemia is an event requiring assistance of another person to actively administer carbohydrate, glucagon, or other resuscitative actions. These episodes may be associated with sufficient neuroglycopenia to induce seizure, unconsciousness, or coma. Plasma glucose measurements may not be available during such an event, but neurological recovery attributable to the restoration of plasma glucose to normal is considered sufficient evidence that the event was induced by a low plasma glucose concentration. The definition of severe symptomatic hypoglycemia includes all episodes in which neurological impairment was severe enough to prevent self-treatment and which were thus thought to place participants at risk for injury to themselves or others. Note that “requiring assistance of another person” means that the participant could not help himself or herself. Assisting a participant out of kindness, when assistance is not required, should not be considered a “requiring assistance” incident.

Severe hypoglycemia will be qualified as an SAE only if it fulfills SAE criteria. For example, events of seizure, unconsciousness, or coma must be reported as SAEs.

- **Documented symptomatic hypoglycemia:** Documented symptomatic hypoglycemia is an event during which typical symptoms of hypoglycemia are accompanied by a measured plasma glucose concentration less than or equal to 3.9 mmol/L ( $\leq 70$  mg/dL). Clinical symptoms that are considered to result from a hypoglycemic episode are, eg, increased sweating, nervousness, asthenia/weakness, tremor, dizziness, increased appetite, palpitations, headache, sleep disorder, confusion, seizures, unconsciousness, or coma.
- **Asymptomatic hypoglycemia:** Asymptomatic hypoglycemia is an event not accompanied by typical symptoms of hypoglycemia but with a measured plasma glucose concentration less than or equal to 3.9 mmol/L ( $\leq 70$  mg/dL).
- **Probable symptomatic hypoglycemia:** Probable symptomatic hypoglycemia is an event during which symptoms of hypoglycemia are not accompanied by a plasma glucose determination, but was presumably caused by a plasma glucose concentration less than or equal to 3.9 mmol/L ( $\leq 70$  mg/dL); symptoms treated with oral carbohydrate.
- **Relative hypoglycemia:** (recently termed “pseudo-hypoglycemia”) is an event during which the person with diabetes reports any of the typical symptoms of hypoglycemia, and interprets the symptoms as indicative of hypoglycemia, but with a measured plasma glucose concentration greater than 3.9 mmol/L ( $> 70$  mg/dL).

In addition to the threshold of plasma glucose of less than or equal to 3.9 mmol/L ( $\leq 70$  mg/dL), documented symptomatic and asymptomatic hypoglycemia with a measured plasma glucose concentration  $\geq 3.0$  -  $< 3.9$  mmol/L ( $\geq 54$  -  $< 70$  mg/dL) and less than 3.0 mmol/L ( $< 54$  mg/dL) will also be analyzed.

Hypoglycemic events will be evaluated regardless of the time of onset during the study and time of the day.

## 2.1.5 Immunogenicity endpoints

### 2.1.5.1 Antidrug (efpeglenatide) antibody

Anti-drug antibody (ADA) is sampled at Visit 3/Week 0, Visit 5/Week 4, Visit 8/Week 12, at the end of treatment visit, and 6 weeks post-treatment follow up visit.

## 2.1.6 Pharmacokinetic endpoints

Pharmacokinetic variables include the concentration of efpeglenatide in the efpeglenatide groups:

- Serum  $C_{\text{trough}}$  of efpeglenatide at predose (Weeks 4, 12, 24, 30)
- Serum concentration of efpeglenatide at postdose (either 4 days [ $\pm 1$  day] after first IMP dose [Week 1], 4 days [ $\pm 1$  day] after 4th dose [Week 4], or 4 days [ $\pm 1$  day] after 12th dose [Week 12] in a subset of participants, approximately 10% of total: [N=16 per group]).

## 2.1.7 Pharmacodynamic/genomics endpoints

Pharmacodynamic parameters are not evaluated in this study.

## 2.2 DISPOSITION OF PARTICIPANTS

This section describes participants' disposition for both participant study status and the participant analysis populations.

Screened participants are defined as any participants who signed the informed consent form.

Randomized participants consist of all participants with a signed informed consent form who have had a treatment kit number allocated and recorded in the IRT database, regardless of whether the treatment kit was used.

The total number of participants in each of the following categories will be presented in the clinical study report using a flowchart diagram or summary table:

- Screened participants
- Nonrandomized but treated participants
- Randomized participants
- Randomized but not treated participants
- Randomized and treated participants
- Participants who have completed the 30-week treatment period as per protocol
- Participants who did not complete the 30-week treatment period, and main reasons for permanently treatment discontinuation
- Participants who completed the study as per protocol

- Participants who discontinued the study by main reason for permanent study discontinuation
- Status at last study contact

For all categories of participants (except for the screened, and nonrandomized but treated categories) percentages will be calculated using the number of randomized participants as the denominator. Reasons for treatment and study discontinuation will be supplied in tables giving numbers and percentages by treatment group. A summary of participants who discontinued treatment and/or study will be provided with reasons for discontinuation, including reasons related to COVID-19.

### **2.2.1 Protocol Deviations**

All significant deviations, potentially impacting efficacy analyses, randomization, drug-dispensing irregularities, and other selected significant deviations will be recorded.

## **2.3 ANALYSIS POPULATIONS**

Participants treated without being randomized will not be considered randomized and will not be included in any efficacy population.

The randomized population includes any participant who has been allocated to a randomized treatment regardless of whether the treatment kit was used or not.

For any participant randomized more than once, only the data associated with the first randomization will be used in any analysis population. The safety experience associated with any later randomization will be assessed separately.

The safety experience of participants treated and not randomized will be reported separately, and these participants will not be in the safety population.

### **2.3.1 Efficacy populations**

The efficacy analysis population will be the intent-to-treat (ITT) population.

#### **2.3.1.1 *Intent-to-treat population***

The ITT population is defined as all randomized participants, irrespective of rescue therapy use and compliance with the study protocol and procedures analyzed according to the treatment group allocated by randomization.

### 2.3.2 Safety population

The safety population is defined as:

- Randomized population who actually received at least 1 dose or part of a dose of the IMP, analyzed according to the treatment actually received.

In addition:

- Nonrandomized but treated participants will not be part of the safety population; however, their safety data will be presented separately
- Randomized participants for whom it is unclear whether they took the IMP will be included in the safety population as randomized
- For participants receiving 1 or more injections of efpeglenatide during the trial, regardless of being assigned to the efpeglenatide groups or not, the treatment group allocation for as-treated analysis will be included in the efpeglenatide dose group that they are exposed for longer duration. In case of a tie, the highest dose group will be used. Participants, who prematurely discontinued study treatment during the titration phase, will be summarized in their planned treatment group for as-treated analysis too.
- Randomized participants will be excluded from the safety population only if there is documented evidence (ie, all study dates recorded as no medication taken) that participants have not taken the study treatment. If a participant is dispensed double-blind IMP and is lost to follow-up without any documented evidence, the participant will be considered exposed.

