4 STUDY DESIGN

4.1 OVERALL DESIGN

The current protocol EFC15337, is a multicenter, randomized, double-blind, placebo-controlled Phase 3 study evaluating the efficacy and safety of efpeglenatide addition in participants inadequately controlled with metformin alone or in combination with SU.

Eligible participants will be randomly assigned to 1 of 3 dose levels of efpeglenatide (2, 4, or 6 mg) or to placebo, to be administered SC once weekly. Randomization will be stratified by HbA1c at screening (<8%, ≥8%) and SU use at screening (Yes/No). Masked weekly dose escalation over the course of 4 weeks will be used to reach the assigned 4 and 6 mg efpeglenatide weekly doses. Escalation will start from 2 mg once weekly to the maximum of 4 or 6 mg once weekly, as assigned at randomization. Participants randomly assigned to the efpeglenatide 2-mg dose arm will also initiate dosing at 2-mg once weekly and remain on this dose for the treatment duration. In order to blind the treatments, both efpeglenatide and placebo will be provided in volume matched PFSs.

The study will be comprised of 3 periods as follows:

- An up to 3-week screening period (with a minimum of 10 days)
- A 30-week double-blind, placebo-controlled treatment period, for efficacy and safety assessments
- A 6-week posttreatment follow-up period to collect safety information after last dose of IMP (treatment completed or permanent IMP discontinuation)

The maximum study duration per participant will be 39 weeks.

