4.3 JUSTIFICATION FOR DOSE

The selection of efpeglenatide 2, 4, and 6 mg once weekly doses is based on the results of early phase studies.

Efpeglenatide has shown increasing efficacy up to the highest dose tested. Both once-weekly 2 mg and 4 mg doses have shown clinically relevant efficacy in study HM-EXC-203. The achieved HbA1c reduction indicates that the dose-response plateau has not been reached with the 4 mg dose so most likely, higher efficacy of the 6 mg dose compared to the 4 mg dose can also be expected for glycemic control in diabetic patients. The once-weekly 6 mg dose tested in non-diabetic subjects in the Phase 2 study (HM-EXC-205) has shown higher efficacy in the decrease of body weight than the once-weekly 4 mg dose in this population.

Nausea and vomiting events appeared to be dose-related and the trend over time showed an increase in incidence after the first injection with a general decrease thereafter for all tested doses. Based on the observed general decrease of GI events incidence after the first week of treatment with efpeglenatide, dose increases to achieve the higher doses of 4 and 6 mg (in the corresponding arm) will be in 2 mg step intervals every 2 weeks in order to minimize the GI adverse effects. The escalation step of 2 mg is small enough to contribute to improvement of GI tolerability at dose increase. With this dose escalation schedule, the dose of 4 mg once-weekly will be achieved 2 weeks after the first dose of efpeglenatide and the maximal dose of 6 mg once-weekly will be achieved only 4 weeks after the first dose of efpeglenatide.

Please refer to the IB for more details (2).

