6.6 DOSE MODIFICATION

Up-titration of IMP from randomization to Week 4 is described in [Table 2](#). From Week 4 (Visit 5) through the rest of the double-blind treatment period, participants will remain on the randomized IMP (efpeglenatide assigned dose or placebo) until the EOT at Week 30 (Visit 12).

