Tipping-point analysis based on the same MI method as described above will be performed to examine the robustness of the results from the primary analysis. A penalty δ will be added to participants in efpeglenatide groups (2, 4, or 6 mg) who have no HbA1c data at Week 30. The penalty will be gradually increased to evaluate at which level the conclusion of the analyses in terms of statistical significance is changed for each efpeglenatide dose group. The tipping point is the penalty level, at which the magnitude of efficacy reduction in participants without HbA1c data at Week 30 creates a shift in the treatment effect of efpeglenatide from being statistically significantly better than placebo to a non-statistically significant effect. Least squares mean difference between each efpeglenatide dose and placebo and its associated p-value will be provided for each penalty level.

Another sensitivity analysis method for the primary efficacy endpoint (change from baseline to Week 30 in HbA1c) will be an ANCOVA model with missing values imputed by control-based MI method (copy to reference) under the missing not at random framework in the ITT

Endpoint

Statistical Analysis Methods

population.

- For participants in the placebo group, missing data will be imputed based on the placebo group data
- For participants in the efpeglenatide group, missing data will be imputed as if the participants were on placebo throughout the study

Each of the complete datasets after the imputation will be analyzed by the ANCOVA model with the treatment groups (efpeglenatide 2, 4, or 6 mg, placebo), randomization stratum of screening HbA1c (<8%, ≥8%), randomization stratum of Screening SU (Yes/No) and country as fixed effects, and baseline HbA1c value as a covariate. Same results as the primary analysis will be provided.

Descriptive analyses will be conducted to explore missing data patterns for HbA1c in the primary efficacy analysis, with number and percentage of participants in each of the following categories presented by treatment group.

- Pattern 1: participants without baseline values, if any
- Pattern 2: participants with baseline values but without postbaseline values during the 30-week treatment period
- Pattern 3: participants with baseline values and at least 1 postbaseline value during the 30-week treatment period but not at Week 30
- Pattern 4: participants with baseline values and a Week 30 value during the 30-week treatment period

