## 1.3 DETERMINATION OF SAMPLE SIZE

The sample size calculations are performed based on the primary efficacy endpoint, change in HbA1c (%) from Baseline to Week 30.

A sample size of 160 per arm (ie, 160 participants for each of the efpeglenatide dose groups and 160 for the placebo group) has >99% power to detect a treatment difference of -0.6% between each dose of efpeglenatide and placebo in HbA1c change from baseline to Week 30, assuming a common SD of 1.1% (2-sided,  $\alpha=0.05$ ) for each comparison. Furthermore, with approximately 50% of participants being on metformin alone (ie, 80 per arm) and approximately 50% on Metformin + SU (ie, 80 per arm), there will be 92% (81%) power to detect a treatment difference of -0.6% (-0.5%) between each efpeglenatide dose and placebo within the subgroup of participants on metformin alone or subgroup of participants on metformin + SU.

Hence, there are 4 parallel dosing arms:

- Efpeglenatide 2 mg, N=160
- Efpeglenatide 4 mg, N=160
- Efpeglenatide 6 mg, N=160
- Efpeglenatide placebo, N=160

Hierarchical procedure will be done to adjust the multiplicity of comparison.

[figure not shown]

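### Could the as-treated rule in SAP 2.3.2 count a correctly dosed 6 mg participant in the 4 mg safety column?

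*SAP*

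**What the plan says.** SAP 2.3.2 analyses the safety population by treatment received. Its allocation rule covers every participant with one or more efpeglenatide injections, whatever their assignment: they are "included in the efpeglenatide dose group that they are exposed for longer duration". It continues: "In case of a tie, the highest dose group will be used". One exemption follows: "Participants, who prematurely discontinued study treatment during the titration phase, will be summarized in their planned treatment group for as-treated analysis too". The section does not say what a *dose group* is, where the *titration phase* begins and ends, or how time at a dose is counted.

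The schedule is in Protocol Table 2. Doses 1 to 5 are 2 mg throughout in the 2 mg arm; 2, 2, 4, 4, 4 mg in the 4 mg arm; and 2, 2, 4, 4, 6 mg in the 6 mg arm. Three Protocol sections bear on when titration ends:

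- Protocol 4.1: "Masked weekly dose escalation over the course of 4 weeks will be used to reach the assigned 4 and 6 mg" doses.
- Protocol 4.3: "the dose of 4 mg once-weekly will be achieved 2 weeks after the first dose of efpeglenatide", with 6 mg reached at 4 weeks.
- Protocol 6.6: "Up-titration of IMP from randomization to Week 4 is described in" Table 2. The next sentence has participants on their randomized product from the Week 4 visit.

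Protocol 7.1.3 restarts titration after three or more consecutive missed doses. The allocation sets the columns of the exposure tables (SAP 2.4.2) and the safety tables (SAP 2.4.4).

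**The concern.** The rule is not limited to dosing errors, and everyone in the 4 and 6 mg arms receives lower strengths first by design. A programmer could therefore add up the time spent at each strength and allocate by the longest. A participant dosed exactly as randomized, who stops just after the first 6 mg injection, would then be shown under 4 mg. One who stops a dose earlier, and never had 6 mg, would stay under 6 mg through the exemption. That is the wrong way round.

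Protocol 4.3 describes nausea and vomiting as apparently dose-related, so a stop soon after a step up is plausible. On this reading that participant's adverse events and exposure time would leave the 6 mg column, and two programmers working from the same text could build different tables.

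**Working it through.** The plan gives no figure for this rule, so there is none to reproduce. The check has two parts: what the dose-strength reading does, and whether it is the reading the documents support.

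**Inputs.** Dose schedule from Protocol Table 2; longest exposure, ties upward, from SAP 2.3.2; duration as last dose date minus first dose date plus 7, from SAP 2.4.2.1. For n uninterrupted weekly doses that is 7(n − 1) + 7 = 7n days, so each dose counts 7 days.

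**Step 1: allocation by strength, before the exemption.**

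| Arm | Stop after dose | Days at 2 / 4 / 6 mg | Longest | Group |
|---|---|---|---|---|
| 6 mg | 3 | 14 / 7 / 0 | 2 mg | 2 mg |
| 6 mg | 4 | 14 / 14 / 0 | tie 2, 4 | 4 mg |
| 6 mg | 5 | 14 / 14 / 7 | tie 2, 4 | 4 mg |
| 6 mg | 6 | 14 / 14 / 14 | three-way tie | 6 mg |
| 4 mg | 3 | 14 / 7 / – | 2 mg | 2 mg |
| 4 mg | 4 | 14 / 14 / – | tie 2, 4 | 4 mg |

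Stops after doses 1 and 2 give 2 mg in every arm. Later stops give the assigned dose. The 2 mg arm never moves.

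**Step 2: apply the exemption under each possible end of titration.**

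- Doses 1 to 4 in every arm: one stop point is left (6 mg arm, dose 5, counted in 4 mg).
- Through the week after the Week 4 dose: none.
- Ending when each arm first receives its assigned dose: two (6 mg arm, dose 5; 4 mg arm, dose 3, counted in 2 mg).

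**Step 3: actual dates.** Let Visit 4 fall on day a (11 to 17) and Visit 5 on day b (25 to 31), the ±3-day windows. A 6 mg participant stopping after dose 5 has a − 1, b − a and 7 days. The 4 mg group results when b − a ≥ a − 1, that is b ≥ 2a − 1. For a = 11 to 17 this holds for 7, 7, 7, 5, 3, 1 and 0 values of b, or 30 of the 49 combinations. The other 19 give 2 mg and none gives 6 mg. Actual dates also blur the edge: with a = 17 there are 16 days at 2 mg, against 14 at 6 mg after dose 6. The counts in Step 2 are therefore for the nominal schedule.

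**Step 4: re-titration, counting doses.** Take the 6 mg arm with three doses missed after dose 7. The doses already given are 2 / 2 / 3 at 2 / 4 / 6 mg. A full restart (2, 2, 4, 4) and one 6 mg dose make 4 / 4 / 4, a tie, so 6 mg. A stop at the second restart dose makes 4 / 2 / 3, so 2 mg unless the exemption covers re-titration.

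**Step 5: what *dose group* means elsewhere.**

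- SAP 1.3 sizes the trial with "160 participants for each of the efpeglenatide dose groups". These are randomized arms.
- Protocol 9.4.1, on the tipping-point analysis, looks for the penalty at which "statistical significance is changed for each efpeglenatide dose group". These are again arms.
- SAP 2.4.4.1 sorts adverse events by incidence in the 6 mg group, a tabulated arm.
- The sentence at issue in SAP 2.3.2 itself speaks of efpeglenatide groups to which participants are assigned.

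The documents do not use the term for a strength passed through during titration. On the arm reading, scheduled lower doses are part of the 4 or 6 mg regimen, and the number of correctly dosed participants who move is zero.

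**The case for a change.** The best case for a change is that SAP 2.3.2 is the only text that fixes these columns and it states no limit to dosing errors. Usage elsewhere is also not a definition. Protocol 6.6 places the Week 4 dose most naturally after up-titration, where the exemption would not apply. Re-titration adds further cases, and one or two sentences would settle everything.

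The missing definitions and the dose-5 arithmetic stand. Three things weaken the rest.

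- The exemption is not evidence for the strength reading. It has a purpose on the arm reading too: doses 1 and 2 are identical in all three arms, and doses 1 to 4 in the 4 and 6 mg arms, so an early stopper's doses do not identify a regimen. Keeping such participants in their planned group also shows that scheduled titration was not meant to move anyone.
- The end of titration is open in both directions. Protocol 6.6 refers to Table 2, whose schedule runs up to and includes the Week 4 column. If that week counts as titration, the dose-5 case disappears even on the strength reading.
- It might be argued that SAP 2.4.2.1 could be applied separately to each strength. In the Step 4 case ending at one 6 mg dose after restart, that gives 84, 84 and 77 days, a sum of 245. The participant's whole exposure is 14 × 7 + 7 = 105 days. The formula is written for total exposure; used per strength it counts overlapping time, so it is not a plausible reading.

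**Conclusion.** No change follows. This is a gap in definitions that an analyst would fill sensibly by keeping participants who received only their assigned regimen, including its titration steps, in their arm. The documents' usage and the exemption both point that way.

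A wrong column arises for a correctly dosed, uninterrupted participant only if the rule is run on strength received and the titration phase is also taken to exclude the week after the Week 4 dose (or, in the 4 mg arm, to end at Week 2). On the nominal schedule that is one or two stop points across all arms. A stop during re-titration could have the same effect, but only on the strength reading and only if re-titration is not exempt. The documents do not say how many participants would stop at those points, so the effect on event rates cannot be stated.

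Whatever the number, the consequence is confined to descriptive exposure and safety tables. SAP 2.4.4 plans no systematic testing, and SAP 1.6 describes a simplified plan for a synopsis report after early termination. The conclusion assumes that allocation is programmed by arm; the safety results would remain sound.
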